5.2.6.2 Adverse event and serious adverse event collection and reporting

The investigator shall maintain and keep detailed records of all AEs in their patient files.

Collection of AEs

The study design is of non-interventional nature regarding study medication and the study is conducted within the conditions of the approved marketing authorisation. Sufficient data from controlled interventional trials are available to support the evidence on the safety and efficacy of the studied BI drug. For this reason the following AE collection and reporting requirements have been defined.

The following must be collected by the investigator from signing the informed consent onwards until the end of the study:

- all Serious Adverse Events (SAEs) (regardless of causality),
- all Non-serious ADRs
- and AESIs

All SAEs, all non-serious ADRs, and AESIs including those persisting after study completion must be followed up until they are resolved, have been sufficiently characterized, or no further information can be obtained.

The investigator carefully assesses whether an AE constitutes an ADR using the information below.

Causal relationship of adverse event

The definition of an adverse reaction implies at least a reasonable possibility of a causal relationship between a suspected medicinal product and an adverse event. An adverse reaction, in contrast to an adverse event, is characterised by the fact that a causal relationship between a medicinal product and an occurrence is suspected.

Medical judgment should be used to determine the relationship, considering all relevant factors, including pattern of reaction, temporal relationship, de-challenge or re-challenge, confounding factors such as concomitant medication, concomitant diseases and relevant history.

Arguments that may suggest a **reasonable causal relationship** could be:

- The event is **consistent with the known pharmacology** of the drug
- The event is known to be caused by or **attributed to the drug class**.
- A **plausible time to onset of the event** relative to the time of drug exposure.

- Evidence that the **event is reproducible** when the drug is re-introduced
- **No medically sound alternative etiologies** that could explain the event (e.g. preexisting or concomitant diseases, or co-medications).
- The event is typically **drug-related and infrequent in the general population** not exposed to drugs (e.g. Stevens-Johnson syndrome).
- An indication of dose-response (i.e. greater effect size if the dose is increased, smaller effect size if dose is diminished).

Arguments that may suggest that there is **no reasonable possibility of a causal relationship** could be:

- No plausible time to onset of the event relative to the time of drug exposure is evident (e.g. pre-treatment cases, diagnosis of cancer or chronic disease within days/weeks of drug administration; an allergic reaction weeks after discontinuation of the drug concerned)
- Continuation of the event despite the withdrawal of the medication, taking into account the pharmacological properties of the compound (e.g. after 5 half-lives).
Of note, this criterion may not be applicable to events whose time course is prolonged despite removing the original trigger.
- Additional arguments amongst those stated before, like alternative explanation (e.g. situations where other drugs or underlying diseases appear to provide a more likely explanation for the observed event than the drug concerned).
- Disappearance of the event even though the study drug treatment continues or remains unchanged.

Intensity of adverse event

The intensity of the AE should be judged based on the following:

- Mild: Awareness of sign(s) or symptom(s) which is/are easily tolerated
Moderate: Enough discomfort to cause interference with usual activity
Severe: Incapacitating or causing inability to work or to perform usual activities

Pregnancy:

In rare cases, pregnancy might occur in a study. Once a subject has been enrolled into the study, after having taken nintedanib, the investigator must report any drug exposure during pregnancy, which occurred in a female subject or in a partner to a male subject to the Sponsor by means of Part A of the Pregnancy Monitoring Form. The outcome of the pregnancy associated with the drug exposure during pregnancy must be followed up and reported by means of Part B of the Pregnancy Monitoring Form.

In the absence of a reportable AE, only the Pregnancy Monitoring Form must be completed, otherwise the NIS AE form is to be completed and forwarded as well within the respective timelines.

Expedited Reporting of AEs and Drug Exposure During Pregnancy

The following must be reported by the investigator on the NIS AE form from signing the informed consent onwards until the end of the study:

Type of Report	Timeline
All Serious Adverse Events (regardless of causality)	immediately within 24 hours
All non-serious ADRs associated with nintedanib	7 calendar days
All pregnancy monitoring forms	7 calendar days

The same timelines apply if follow-up information becomes available for the respective events. In specific occasions the Investigator could inform the Sponsor upfront via telephone. This does not replace the requirement to complete and **submit** the NIS AE form.

Information required

For each reportable adverse event, the investigator should provide the information requested on the NIS AE form.

5.2.6.3 Reporting to health authorities

Adverse event reporting to regulatory agencies will be done by the MAH according to local and international regulatory requirements.

5.3 DRUG CONCENTRATION MEASUREMENTS AND PHARMACOKINETICS

5.3.1 Assessment of pharmacokinetics

Not applicable, there are no pharmacokinetic assessments planned for this trial.

5.3.2 Methods of sample collection

Not applicable, there are no pharmacokinetic assessments planned for this trial

5.3.3 Analytical determinations

Not applicable, there are no pharmacokinetic assessments planned for this trial.

5.3.4 Pharmacokinetic – pharmacodynamic relationship

Not applicable, there are no pharmacokinetic assessments planned for this trial.

5.4 ASSESSMENT OF BIOMARKER(S)

Not applicable, there are no biomarker assessments planned in this trial.

5.5 OTHER ASSESSMENTS

No other assessments are planned for this trial.

5.6 APPROPRIATENESS OF MEASUREMENTS

All measurements conducted for primary and secondary endpoints are using standard methods.

6. INVESTIGATIONAL PLAN

6.1 VISIT SCHEDULE

This trial consists of two parts, a screening and an interventional period. The screening period consists of the time between signing consent and randomization, and will last a minimum of 7 days. The interventional period consists of the time from randomization through the week 24 assessment visit.

There are two screening visits (Visit 1, which must be preceded by a separate informed consent Visit 0) and 6 visits (Visits 2 to 7) planned within the 24 week interventional period. There is no follow up period in this trial.

After giving his/her informed consent, the patient will be screened for inclusion (see [Section 3.3.2](#) and exclusion criteria (see [Section 3.3.3](#)) for the trial at Visits 0, 1 and Visit 2 (refer to [Flowchart](#)).

The patient will be dispensed an activity monitor and ProActive tool (eDiary) at the consent visit, and will wear the activity monitor and use the eDiary for 7 days prior to Visit 1 for training purposes.

Visit 2 can be performed once the results from local laboratory of Visit 1 are obtained and the patient has worn the activity monitor and completed the eDiary for 7 days. If for any reason the screening phase for an individual patient lasts for more than 6 weeks, then the laboratory examination for Visit 1 has to be repeated before randomization. The patient will be randomized at Visit 2 if all inclusion and none of the exclusion criteria are fulfilled. Central HCRT is not required prior to randomization, but if historical HRCT is not available to be sent for central calculation of QLF, a scan should be obtained after screening/consent at the latest 7 days after Visit 2.

On treatment visits will be performed at 3, 6, 12, 18 and 24 weeks. Procedures for these visits are outlined in the flow chart and detailed instructions are available in [Section 5](#), select appendices and the ISF, as applicable.

Visit 7 is the end of treatment visit, there is no follow up period. Visit 7 procedures should be followed for early termination visits if possible.

If a patient misses a visit, the visit should be rescheduled as soon as possible. If unable to reschedule, the clinical monitor should be contacted.

6.2 DETAILS OF TRIAL PROCEDURES AT SELECTED VISITS

6.2.1 Screening and run-in period(s)

Screening Period

Visit 0 - Informed consent (at least 7 days before Visit 1)

- Informed consent will be obtained prior to patient participation in the trial, which includes any medication wash-out procedures or restrictions as well as HRCT transfer to central review. Upon obtaining informed consent, the patient will be instructed on the medication washout and other restrictions needed, and dispensed an eDiary (or eDiary application for own device) and activity monitor if they meet the inclusion and exclusion criteria at this time.
- A preliminary check of in-/exclusion criteria is recommended at time of informed consent to avoid unnecessary procedures in non-eligible patients. Confirmation that the patient **is being treated with nintedanib for up to 30 months** will be confirmed via medical records, observation of the patient prescription medication, or medical records will be requested to confirm. **Patients who have recently started nintedanib 150 mg BID and have started by the day of randomization must be on nintedanib 150 mg BID a minimum of 10 days by the first day of pulmonary rehabilitation.**
- An HRCT not older than 24 months will be sent for central calculation of QLF, to assess HRCT pattern for patient characterization. Provided the patient meets all other eligibility criteria, the HRCT can be performed for the purposes of participation in the trial if the patient does not have a HRCT within 24 months, at the time of the scheduled Visit 2.
- Site personnel will perform a screening call in IRT to ensure accurate tracking of trial participation.

Visit 1

- Demographics
- Medical history including pre-existing conditions
- Medication records needed for confirmation that the patient has been **treated with nintedanib for up to 30 months** will be reviewed at this visit if not available at consent visit. **Patients who have recently started nintedanib 150 mg BID and have started by the day of randomization must be on nintedanib 150 mg BID a minimum of 10 days by the first day of pulmonary rehabilitation.**
- Any adverse events (since consent, if applicable)
- SGRQ, KBILD and UCSD SOBQ will be completed by the patient, prior to any procedures
- Collect and download/review PROactive Tool from eDiary and activity monitor data
- Physical examination including vital signs

- A resting 12-lead electrocardiogram using site's own equipment will be performed and evaluated by the Investigator (if possible prior to blood draw)
- Resting SP02
- FVC measurements will be conducted using the site's own equipment, per the instructions in [Section 5.1.2.3](#)
- DLco measurement will be conducted. FVC measurement has to be done first, followed by patient's rest and subsequent DLco measurement
- Blood and urine samples (safety lab and serum pregnancy if woman of child bearing potential) will be collected and submitted to the local laboratory (for details refer to [Section 5.2.3](#)). Prior to blood draw a pre-assessment of all inclusion and exclusion criteria is highly recommended
- Practice 6 minute walk test
- Incremental and practice work rate cycle ergometry test performed at the clinic at end of Visit 1 [REDACTED]
- Send HRCT to central calculation of QLF if available, or schedule patient for HRCT if not available
- For patients qualified to enter the screening period, patients will be dispensed an eDiary (or eDiary application for own device) and activity monitor and instructed on the use of both devices, with specific instructions given to use both devices for 7 days prior to Visit 2
- Visit 2 will be scheduled
- If patient fails screening, IRT call to discontinue patient

6.2.2 Treatment period(s)

Treatment phase will be a 24 week period, beginning at visit 2.

Visits are planned after 3, 6, 12, 18 and 24 weeks after randomization. If additional time is needed after randomization to schedule the pulmonary rehabilitation for a patient randomized to that group, the time between visits 2 and 3 may be extended up to 6 weeks. The visit schedule will resume on the day of the first pulmonary rehabilitation visit, and all subsequent visits will be scheduled accordingly to keep the time between visits per protocol and a total 24 week treatment period.

During all the visits it is important that patients' questionnaires are completed before any other procedure. The order of the other procedures to be followed is given below as an indication but can be adapted for practical reasons.

Visit 2

- SGRQ, KBILD and UCSD SOBQ
- Adverse events and concomitant therapy assessment since last visit
- Download/review PROactive Tool and activity monitor results
- Physical examination including vital signs
- Resting SpO₂
- Blood samples for laboratory tests
- Urinary pregnancy test
- Pulmonary function test including FVC
- DL_{CO}
- Assessment of in/exclusion criteria
- Randomisation via IRT
- 6 minute walk test
- [REDACTED]
- Schedule patient for pulmonary rehabilitation if randomized to that treatment group
- Schedule Visit 3
- Send HRCT for calculation of QLF if not previously available.

Visits 3, 4, 5 and 6:

- Adverse events and concomitant therapy assessment since last visit
- Collect and download/review PROActive Tool from eDiary and activity monitor data at Visit 5
- Review pulmonary rehabilitation attendance with patient and record information from pulmonary rehabilitation reports into eCRF for patients in the PR treatment group at Visits 3, 4 and 5
- Physical examination including vital signs
- Blood samples for laboratory tests
- Urinary pregnancy test
- SGRQ, KBILD and UCSD SOBQ at Visit 5
- Pulmonary function test including FVC at Visit 5
- DLCO at Visit 5
- SP02 at Visit 5
- Six minute walk test at Visit 5
- [REDACTED]
- Instruct patient on activity monitoring and eDiary (or eDiary application for own device) and remind patient they need to pick up or will receive device in the mail to allow 7 days of use prior to next visit at Visits 4 and 6
- Schedule next visit.

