	
 • Absolute change from baseline of FVC and FVC % predicted • Relative change from baseline of FVC and FVC % predicted • Absolute categorical change of FVC % predicted up to 12 and 24 weeks: decrease by >5%, increase by >5%, and change within ≤ 5 • Absolute categorical change of FVC% predicted up to 12 and 24 weeks: decrease by >10, increase by >10, and change within ≤ 10 
○ Change from baseline in daily accelerometer activity from baseline at 12 and 24 weeks
 
[REDACTED]

Safety criteria:
	
 • Vital signs, physical examination, weight • Clinical laboratory tests (haematology, clinical chemistry, and urinalysis) • Reporting of adverse events • 12 lead electrocardiogram

Statistical methods:
	
The primary (6MWD at 12 weeks) will be analysed using the Analysis of Covariance model including intervention as a fixed categorical covariate and baseline 6MWD as continuous covariate
 
6MWD will be analysed on the original scale. [REDACTED]
 
[REDACTED] all other assessments will be analysed using original scales.

	
For secondary [REDACTED] endpoints, 12-week endpoints will be analysed using similar ANCOVA methodology as the primary endpoint. The 24-week endpoints will be analyzed using a mixed model with repeated measures.
 
Descriptive statistics will be shown for all efficacy and safety endpoints.

--	---

FLOW CHART

	Screening		Interventional Period					
	0	1	Treatment					
Visit	0	1	2	3	4	5	6	7 (EOT)
Weeks of treatment	-2	-1	0	3	6	12	18	24 ⁶
Day	At least 7 days before visit 1	≥ 7d before V 2	1	22	43	85	127	169
Time window				±3	±3	±3	±3	±7
Informed consent	X*							
Demographics/ baseline conditions		X						
Medical history		X						
In-/exclusion criteria	X	X	X					
Physical examination ⁷ , vital signs		X	X	X	X	X	X	X
Laboratory test		X	X	X	X	X	X	X
Pregnancy test		X	X	X	X	X	X	X
Spirometry (FVC)		X	X			X		X
SpO ₂ (peripheral capillary oxygen saturation)		X	X			X		X
DL _{CO}		X	X			X		X
HRCT sent for outcomes review ¹		X ¹	X ¹					
12-lead electrocardiogram (ECG)		X						X
(Practice) Six-minute walk test		X						
Six minute walk test			X			X		X
		■	■			■		■
Instruct Patient on Activity Monitoring and PROactive tool (eDiary) ²	X	X	X		X		X	
Activity Monitoring (Dynaport)	X	X	X			X		X
SGRQ, KBILD, UCSD SOBQ		X	X			X		X
PROactive Tool ^{2,3}	X	X	X			X		X
Randomisation			X					
Schedule pulmonary rehab days for assigned patients ⁶			X					

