4.1.5 Blinding and procedures for unblinding

4.1.5.1 Blinding

Qualified subjects will be randomized at Visit 2 to either continue with their usual treatment or to add a pulmonary rehabilitation program to their usual treatment. In this open-label trial, treatment allocation will not be concealed throughout the trial. The CRF will contain information on randomised treatment. As patients are randomized to either no pulmonary rehabilitation or pulmonary rehabilitation, it is not possible to blind the treatments in this trial.

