5.1.2 Assessment of efficacy

5.1.2.1 6 Minute walk test

The distance measured in the 6 Minute Walk Test at 12 and 24 weeks will be assessed according to the procedures described in [Appendix 10.1](#).

Four 6 MWTs will be performed during the trial (one practice and three tests). At Visit 1 a practice 6 MWT, also referred to as the Titration Walk Test, will be conducted to acquaint the patient with the procedure and to determine the level of oxygen needed for subsequent testing. As per inclusion criterion #8, patients must be physically able to perform a 6MWT, as per the instructions. Patients who cannot complete the Titration Walk Test will be considered a Screen Failure. Three 6 MWTs will be conducted during the randomized treatment phase at Visits 2 (baseline), 5 and 7 (End of Treatment). During the 6 MWT, the Borg Scale will be administered. Detailed instructions for the conduct of the 6 MWT and Borg Scale are provided in the ISF and Appendix 10.1 and [10.2](#) and in the distributed instructional video. It is important the instructions are followed exactly. The test will be performed at approximately the same time each day from time of Visit 2 testing. Patients who cannot complete the 6MWT after randomization will remain in the trial.

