5.1.2.2 Change in quality of life

Change from baseline in QoL will be measured using the SGRQ, KBILD, and UCSD-SOBQ questionnaires at 12 and 24 weeks. The questionnaires are described in [Appendix 10.3](#), [10.5](#) and [10.6](#). The questionnaires should be completed first during the study visit, prior to pulmonary function testing and other procedures. The questionnaires will be completed at Visits 1, 2, 5 and 7.

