10.1.2 Six-minute walk test

A full description of the six minute walk test will be provided in both the instructions and instructional video.

Testing should be performed in a location where a rapid, appropriate response in the event of an emergency is possible and emergency instructions in the manual should be followed.

[figure not shown]
During the 6-MWT patients will be monitored for both HR and SpO₂ using pulse oximeter.

[figure not shown]
If SpO₂ decreases to below 80% at any time after the patients begins walking, first ensure the oximeter is connected and working properly and ensure that a confident pulse signal is generated. If SpO₂ is still below 80%, stop the study and allow the subject to sit and rest, the study is complete.

[figure not shown]
The distance walked will be measured in feet (f) and will be recorded. If the test is stopped prematurely, the distance (f), the duration (min), and the reason for stopping will be recorded.

[figure not shown]
Patients will be asked to rate the intensity of dyspnea (shortness of breath) and fatigue using the Modified Borg Scale (see [Section 10.2](#)) as described in the instructions.

Assessments will be recorded in a worksheet during the testing, and transferred to the eDC system.

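### The Visit 2 list places randomisation directly before the baseline six-minute walk in an open-label trial, and neither document requires the walk to come first

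*Protocol*

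**What the plan says.** Protocol 6.2.2 lists the Visit 2 procedures. After the eligibility check comes "Randomisation via IRT", and the item directly below it is the six-minute walk. Questionnaires must precede everything else; for the rest, "The order of the other procedures to be followed is given below as an indication but can be adapted for practical reasons". Protocol 4.1.5.1 states: "In this open-label trial, treatment allocation will not be concealed throughout the trial".

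Where order is thought to matter, it is set. Protocol 5.1.2.2 says: "The questionnaires should be completed first during the study visit, prior to pulmonary function testing and other procedures". Section 5.1.2.3 puts resting SpO2 before FVC and DLco after it, and section 5.2.3 puts blood sampling before exercise testing. None of these rules mentions randomisation.

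The Visit 2 walk is the baseline (Protocol 5.1.2.1). It is subtracted in the primary endpoint and is the covariate in the planned ANCOVA (Protocol 7.3.1). Operational detail is held elsewhere: "A full description of the six minute walk test will be provided in both the instructions and instructional video". Of those materials Protocol 5.1.2.1 says: "It is important the instructions are followed exactly".

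**The concern.** Walking distance depends on effort, and Protocol 10.1.1 itself says that psychological factors affect exercise performance. A patient who has just learned that they will, or will not, receive rehabilitation may walk differently. A baseline taken at that point can be influenced by the assignment, so it is no longer a pre-randomisation measurement. Any such shift goes straight into the change score, and adjusting for that baseline carries most of it into the ANCOVA contrast.

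Among the efficacy measures visible in the Visit 2 list, only the walk, the primary one, stands after randomisation. FVC and DLco stand before it, although their place is also only indicative. Since SAP 4 and 7.4.1 now limit the primary endpoint to descriptive statistics, the raw change is what will be reported.

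**Working it through.** **1. Does any other text fix the order?**

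- Protocol flow chart: the walk row is above the randomisation row, the reverse of 6.2.2. Both are marked for Visit 2, and no order within a visit is stated.
- Protocol 3.3.2, criterion 8: requires the practice walk only.
- Protocol 5.1.2.1, 6.1 and 7.3.1: baseline is tied to Visit 2 and to Day 1 of a period that begins at randomisation. None says whether the walk precedes the IRT call.
- SAP 6.7: baseline is the last assessment up to and including the start of the treatment period, with a window ending on Day 1 inclusive. A same-day walk after the call still counts.
- Protocol 10.1.1 controls motivational cues, and the Borg text in 10.2 mentions a tester who is blinded. Neither hides the arm from the patient.

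So a walk after assignment is permitted, and is the listed sequence, but is not certain at any given site.

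**2. Planned precision (Protocol 7.7).** Inputs: difference 30 m, SD 85 m, two-sided 5%, 80% power. The two-sample t-test gives 126.99, so 127 per arm and 254 in total, as the protocol states. Standard error of the raw difference = 85 × √(2/127) = 10.7 m.

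**3. Illustration of size.** Every input in this step is assumed:

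- s: shift in the rehabilitation arm's mean baseline from knowing the arm, −15 to +15 m, zero included (signs reverse if the control arm shifts)
- f: share of that arm walking after the IRT call
- b: slope of week-12 distance on baseline, 0.6 to 0.9
- p: fraction of s still present at week 12, whatever the walk order

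The observed baseline moves by f·s and week 12 by p·s. Hence:

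- raw bias = (p − f)·s
- ANCOVA bias = (p − b·f)·s
- with the walk first (f = 0), both equal p·s
- the part due to walk order is −f·s raw and −b·f·s ANCOVA

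Size of the order part at |s| = 15 m:

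- f = 1: 15 m raw, which is 15/30 = 50% of the target and 15/10.7 = 1.4 standard errors. ANCOVA: 0.6 × 15 = 9 m to 0.9 × 15 = 13.5 m.
- f = 0.5: 7.5 m raw; ANCOVA 4.5 to 6.75 m.
- f = 0: none.

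Net bias in metres at f = 1, s = +15, relative to an effect free of awareness:

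| p | Raw, listed order | ANCOVA, listed order | Either, walk first |
|---|---|---|---|
| 0 | −15 | −9 to −13.5 | 0 |
| 0.5 | −7.5 | −1.5 to −6 | +7.5 |
| 1 | 0 | +1.5 to +6 | +15 |

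Reordering lowers the absolute net bias only if p < f/2 (raw) or p < b·f/2 (ANCOVA). At f = 1 these limits are 0.5 and 0.30 to 0.45.

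**4. Precision of a retrospective check.** For Visit 2 minus Visit 1 distance compared between arms, the 95% half-width is 1.96 × SD × √(2/n). With an assumed SD of 20 to 50 m it is 4.9 to 12.3 m at 127 per arm, and 10.1 to 25.3 m at an assumed 30 per arm.

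**The case against.** The strongest reply has four parts.

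- **The order is optional, and the operative walk instructions were not available.** Both are true. The instructions may already settle the matter, in which case 6.2.2 should cite them and its list should be corrected to match.
- **The trial was terminated and the ANCOVA dropped.** Also true. The ANCOVA figures describe the protocol's plan only, and 127 per arm may not have been reached. The raw change is still to be reported, and it carries the full baseline shift.
- **The magnitudes are assumed, and reordering can increase net bias.** This stands. If awareness moved the baseline and week-12 walks equally, the listed order would cancel the shift in the raw change, and walking first would leave all of it. Nothing in the documents says which value of p is likelier. The argument therefore rests on having a baseline that assignment cannot touch, not on a promised reduction in bias.
- **SAP 6.7 goes further than being silent.** In the rehabilitation arm the treatment period starts at the first rehabilitation session, which scheduling may delay after Visit 2. A late walk in that interval would qualify as baseline. No walk is scheduled there, so this does not alter the finding, but it supports adding a line to the SAP.

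**Conclusion.** The concern holds. The protocol's listed sequence takes the primary-endpoint baseline after open assignment, and neither document requires otherwise. Confidence in that reading is high; whether the separate walk instructions set an order is unknown.

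Size and direction cannot be derived from the documents. Under the assumed range, walk order contributes between nothing and 15 m in either direction to the raw comparison. This should be fixed because the affected value is central to the primary endpoint and the correction is simple; no particular bias has been shown.

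**What to change.** **Protocol.** In 6.2.2, list the Visit 2 walk before the IRT call. Require the Visit 2 efficacy baselines (walk, spirometry, DLco, questionnaires) to be complete before that call. Leave out the HRCT, which section 6.1 allows up to 7 days after Visit 2. If the walk instructions already fix this order, cite them. Add a matching line to SAP 6.7 that the baseline walk precedes randomisation.

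**Gap to reconcile.** Protocol 5.1.2.1 says of Visit 1: "Patients who cannot complete the Titration Walk Test will be considered a Screen Failure". It separately keeps in the trial those who cannot complete a walk after randomisation. A Visit 2 walk done before randomisation falls under neither rule, and the sponsor must reconcile the text.

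**Walks already done.** If walk and IRT times exist, report by arm how many baseline walks followed randomisation, beside the descriptive change. Protocol 10.1.2 lists no start time among the recorded items, so this may be impossible. Failing that, if Visit 1 distances are in the database, tabulate Visit 2 minus Visit 1 distance by arm. Every randomised patient should have completed the Visit 1 walk, it always precedes assignment, and learning and oxygen titration should affect both arms alike. In a small sample this table is imprecise, and a null result would say little.

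**Cost.** No extra test or visit, and slightly less freedom of order at Visit 2. The change does not remove any awareness effect at week 12 and cannot repair completed walks.
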